8.1 Data Processing and Transmission

All data will be recorded in a SAS® data set format using Data Management Center (SAS 9.3 or higher version).

8.2 Record Lock and Data Export

When subjects complete the trial, their CRFs will be subjected to auditors to verify the data. Once the data from each subject is verified, the data managers will lock all data files. After all data is locked, data managers will be responsible for importing the data sets into the designated database and transferring the data sets to statistical staff members for statistical analysis.

9. Statistical analysis

9.1 Case distribution

Descriptive statistical analysis will be performed for all enrolled cases, randomized cases, completed cases, and uncompleted cases, classified according to whether they meet the inclusion and exclusion criteria, whether they have signed the informed consent form, and other classifications. The data from enrolled subjects will be also used to conduct descriptive statistical analysis according to the definitions of FAS, PPS and SS. The frequency and constituent ratio will be used when appropriate.

9.2 Important Protocol Deviations

Important Protocol Deviations (IPD) will be described using cases and composition ratios. The IPD for each enrolled subject will be listed.

9.3 Processing of Missing Values

Results will be carried forward when primary outcome measures are absent, according to the following details:

-
1. If patients lack a fat attenuation value at the 6 months follow up and they do not show a response at the cessation of therapy, the results at cessation of therapy can be carried forward to the 6 months follow up.
 2. If patients withdraw from the study before cessation of the study, and continue without a response, the results of the last visit can be carried forward.
 3. If patients lack an intermediate visit of a fat attenuation value, but have results for insulin resistance, intestinal barrier function, and intestinal bacterial overgrowth, the previous results can be carried forward.
 4. If patients withdraw from the study because of a full recovery, the results of the last visit can be carried forward.

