4.4. To evaluate the therapeutic effects of Compound Zhenzhu Tiaozhi capsules on NAFLD

1) To assess whether the content of intrahepatic fat will decrease after 1 month, 3 months, and 6 months of Compound Zhenzhu Tiaozhi capsule therapy.

i. Compare the therapeutic effects of Compound Zhenzhu Tiaozhi capsules at 1 month, 3 months, and 6 months with the baseline (pre-vs.post-therapeutic effects of Compound Zhenzhu Tiaozhi capsules).

ii. Compare the therapeutic effects in the Compound Zhenzhu Tiaozhi capsule group with that of the other three groups at parallel time points (Compound Zhenzhu Tiaozhi capsules vs. Conventional drugs).

2) To assess whether NAFLD-FS will be alleviated after 1 month, 3 months, and 6 months of Compound Zhenzhu Tiaozhi capsule therapy.

i. Compare the therapeutic effects of Compound Zhenzhu Tiaozhi capsules at 1 month, 3 months, and 6 months with the baseline (pre- vs. post-therapeutic effects of Compound Zhenzhu Tiaozhi capsules).

ii. Compare the therapeutic effects in the Compound Zhenzhu Tiaozhi capsule group with those of the other three groups at parallel time points

(Compound Zhenzhu Tiaozhi capsules vs. Conventional drugs).

3) To assess whether insulin resistance will be improved after 1 month, 3 months, 6 months of Compound Zhenzhu Tiaozhi capsule therapy.

- i. Compare the therapeutic effects of Compound Zhenzhu Tiaozhi capsules at 1 month, 3 months, and 6 months with the baseline (pre- vs. post-therapeutic effects of Compound Zhenzhu Tiaozhi capsules).
- ii. Compare the therapeutic effects in the Compound Zhenzhu Tiaozhi capsule group with those of the other three groups at parallel time points (Compound Zhenzhu Tiaozhi capsules vs. Conventional drugs).

4) To assess whether the lipids profile in peripheral blood and liver biochemical parameters (ALT, AST, GGT) will be reduced after 1 month, 3 months, and 6 months of Compound Zhenzhu Tiaozhi capsule therapy.

- i. Compare the therapeutic effects of Compound Zhenzhu Tiaozhi capsules at 1 month, 3 months, and 6 months with the baseline (pre- vs. post-therapeutic effects of Compound Zhenzhu Tiaozhi capsules).
- ii. Compare the therapeutic effects in the Compound Zhenzhu Tiaozhi capsule group with those of the other three groups at parallel time points (Compound Zhenzhu Tiaozhi capsules vs. Conventional drugs).

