4.5 In the Compound Zhenzhu Tiaozhi capsules group, firstly calculate the changes in the related parameters of NALFD and the changes in the function of intestine microbiota, then evaluate whether the two changes are related to each other.

1) Analyze the relationship between the changes in DAO, D-lac, LPS, intestinal barrier dysfunction grade I, II, III, IV and the reduction in intrahepatic fat at 1 month, 3 months, and 6 months of Compound Zhenzhu Tiaozhi capsule therapy (possible results: unrelated, positively related, or negatively related).

2) Analyze the relationship between the change in SIBO and the reduction in intrahepatic fat at 1 month, 3 months, and 6 months of Compound Zhenzhu Tiaozhi

capsule therapy (possible results: unrelated, positively related, or negatively related).

3) Analyze the relationship between the changes in DAO, D-lac, LPS, intestinal mucosal barrier dysfunction I, II, III, IV and the improvement of insulin resistance at 1 month, 3 months, and 6 months of Compound Zhenzhu Tiaozhi capsule therapy (possible results: unrelated, positively related, or negatively related).

4) Analyze the relationship between the change in SIBO and the improvement of insulin resistance at 1 month, 3 months, and 6 months of Compound Zhenzhu Tiaozhi capsule therapy (possible results: unrelated, positively related, or negatively related).

5) Analyze the relationship between changes in DAO, D-lac, LPS, intestinal mucosal barrier dysfunction I, II, III, IV and the changes in the lipids profile in peripheral blood and liver biochemical parameters (ALT, AST, GGT) at 1 month, 3 months, and 6 months of Compound Zhenzhu Tiaozhi capsule therapy (possible results: unrelated, positively related, or negatively related).

6) Analyze the relationship between the change in SIBO and the changes in the lipids profile in peripheral blood and liver biochemical parameters (ALT, AST, GGT) at 1 month, 3 months, and 6 months of Compound Zhenzhu Tiaozhi capsule therapy (possible results: unrelated, positively related, or negatively related).

7) Analyze the relationship between changes in DAO, D-lac, LPS, intestinal mucosal barrier dysfunction I, II, III, IV and the change in NAFLD-FS at 1 month, 3 months, and 6 months of Compound Zhenzhu Tiaozhi capsule therapy (possible results: unrelated, positively related, or negatively related).

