4.1 The Primary Efficacy Parameters

Fat attenuation index: The fat attenuation index will be used to assess the therapeutic efficacy. A normal fat attenuation index is defined as < 240 db/m, mild is 240-264 db/m, moderate is 265-294 db/m, and severity is > 295 db/m. We will detect the fat attenuation index at 0, 1, 3, 6 months following treatment. Effective: fat attenuation index is reduced by a level or more (example: moderate to mild). Invalid: fails to meet the effective standard.

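### SAP 9.3 rule 3 allows a carried-forward liver-fat value at month 1 or 3 where gut markers were measured, and nothing keeps those fills out of the gut-liver change analysis

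*SAP*

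**What the plan says.** SAP section 9.3 sets out how missing values are handled and opens with its scope: "Results will be carried forward when primary outcome measures are absent". Its third rule covers patients who are still being followed: "If patients lack an intermediate visit of a fat attenuation value, but have results for insulin resistance, intestinal barrier function, and intestinal bacterial overgrowth", in which case "the previous results can be carried forward". The wording permits the fill; it does not require it.

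The measurement schedule is in SAP section 4.1: "We will detect the fat attenuation index at 0, 1, 3, 6 months following treatment". The intermediate visits are therefore months 1 and 3. The same section rates a patient Effective only if the index falls by at least one severity level, and Invalid otherwise.

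Protocol section 4.5 plans a change-on-change analysis in the capsule group: "firstly calculate the changes in the related parameters of NALFD and the changes in the function of intestine microbiota", then see whether the two are related. Items 1 and 2 relate changes in DAO, D-lactate, LPS, barrier grade and SIBO to "the reduction in intrahepatic fat at 1 month, 3 months, and 6 months of Compound Zhenzhu Tiaozhi capsule therapy". Protocol section 4.4 uses the same visits for arm comparisons and for within-group change: "To assess whether the content of intrahepatic fat will decrease after 1 month, 3 months, and 6 months", with the reference point given as "Compare the therapeutic effects of Compound Zhenzhu Tiaozhi capsules at 1 month, 3 months, and 6 months with the baseline". Section 4.5 does not state its own reference point.

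**The concern.** Rule 3 is triggered where the gut and insulin results exist and the liver-fat value does not. Each such visit can give section 4.5 a pair made of a measured gut change and an unmeasured liver-fat change. A gut result is no evidence that liver fat stayed where it was at the last scan.

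The relation between improvement in NAFLD and change in intestinal function is part of the objective in Protocol section II, and section 4.5 lists absence of a relation as one possible result. A rule that weakens a true association makes that result more likely. In the arm comparisons of Protocol 4.4, every filled month 1 patient counts as a non-responder whatever the liver fat actually did.

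Because the rule is permissive, whether to fill is also left open in an open-label trial.

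**Working it through.** **No figure to reproduce.** The plan states no rate of missed intermediate scans, no expected correlation, and no mean or standard deviation of the liver-fat change. These are assumptions below and are shown over a range.

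**Step 1: what the fill produces.**
- Month 1 missed: the previous value is month 0. Change from baseline = month 0 value − month 0 value = 0. No level is lost, so the rating is Invalid with certainty.
- Month 3 missed, month 1 present: the filled change is the month 1 change, which is stale but generally not zero. A patient rated Effective at month 1 stays Effective.
- Months 1 and 3 both missed: the month 3 fill is again baseline, so the change is zero.
- Month 6: not an intermediate visit, so rule 3 does not apply.

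**Step 2: effect on the month 1 correlation.** Let X be the gut change, Y the true liver-fat change, r their correlation, f the fraction of pairs filled with zero, and m = mean(Y)/SD(Y). If filling is independent of X and Y:
- covariance after filling = (1−f) × cov(X,Y)
- variance after filling = (1−f) × var(Y) + f(1−f) × mean(Y)²
- correlation after filling = r × sqrt[(1−f)/(1+f m²)]

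For m = 1:
- f = 10%: sqrt(0.90/1.10) = 0.905, so 0.40 becomes 0.362
- f = 20%: sqrt(0.80/1.20) = 0.816, so 0.40 becomes 0.327

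Multiplying factor over a wider range:

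| f | m = 0 | m = 0.5 | m = 1 |
|---|---|---|---|
| 5% | 0.975 | 0.969 | 0.951 |
| 10% | 0.949 | 0.937 | 0.905 |
| 20% | 0.894 | 0.873 | 0.816 |
| 30% | 0.837 | 0.807 | 0.734 |

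A simulation of 2,000,000 draws returned the same 0.362 and 0.327.

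**Step 3: month 3.** Simulation with the month 1 change carried forward, assuming a month 1 to month 3 correlation of 0.5 to 0.7 and m of 0.5 to 1: at 20% filled, a true correlation of 0.50 becomes 0.44 to 0.47. The zero fill at month 1 takes the same 0.50 to 0.41 to 0.44.

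**Step 4: is filling better than leaving the pair out?** Take 44 patients (the evaluable number per group in SAP section 3.4), r = 0.40, 20% of month 1 scans missing at random, m from 0.5 to 1, and a two-sided Pearson test at 0.05:
- nothing missing: power 78%
- observed pairs only: power 68%, with the average correlation essentially unchanged
- zero fill: power 59% to 65%, with the correlation attenuated

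With a true correlation of zero, the false-positive rate under the fill is 4.9% to 5.2%. Under random missingness the fill can hide an association but does not create one.

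**The case against.** Several points on the other side have weight.

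- **Section 9.3 is written for the primary outcome.** No sentence sends filled values into section 4.5, and a reader might wrongly infer that the plan definitely does so. The documents support only that it is not prevented: the available SAP text, which ends with section 9.5, has no separate missing-data rule for the section 4.5 analysis. That intrahepatic fat there means the fat attenuation index is a reasonable reading, but it is not stated.
- **Not every fill is a zero.** It is tempting to say that the rule invents zero changes throughout. That is exact at month 1 only; Step 1 shows why it normally fails at month 3.
- **The trigger has an ordinary reading.** Requiring the other results may simply confirm that the patient attended and only the scan is missing. This stands as a motive, but it does not make the previous value a good estimate of the current one.
- **The event may be uncommon.** Protocol section 4.2 under Prescriptions lists Fibrotouch, barrier function and breath test together, and section 4.3 there has them repeated at one month. The planned 10% loss to follow-up is a different event and cannot stand in for f. At f = 5% and m = 1, 0.40 becomes only 0.38. Even the 0.04 shift at f = 10% is small beside a standard error of about 0.13 for r = 0.40 with 44 patients.
- **The formula has limits.** It is a Pearson result under random missingness. Barrier grade is ordinal, and section 4.5 names no correlation method. If missingness depends on response, observed pairs may be biased too.
- **Non-response for a missing value is a common conservative convention.** That defends a stated responder rule. It does not support placing the same value in a change-on-change correlation. The documents also give no reason to expect one arm to miss more scans, so a bias between arms cannot be asserted.

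**Conclusion.** The concern holds in a limited form. Rule 3 permits a fill that sets the month 1 liver-fat change to exactly zero and normally makes the month 3 change stale, at visits where gut markers were measured, and the plan does not exclude those values from section 4.5.

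Under random missingness the month 1 correlation is multiplied by about 0.91 to 0.95 at 10% filled and 0.82 to 0.89 at 20%, for m between 0 and 1. Month 3 is affected less. On these assumptions the fill is worse than omitting the pair, because it adds bias and gives lower power.

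The size rests on assumed values of r, m and f, on random missingness, and on reading intrahepatic fat as the fat attenuation index. If missingness depends on response, the direction of bias is unknown. A reader might go further and conclude that the rule creates false associations or alters the month 6 result. The first does not follow under random missingness, and the second is outside the reach of rule 3.

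**What to change.** 1. State in the SAP that the Protocol 4.5 analyses use only visits at which both the fat attenuation value and the gut marker were measured, and that change is taken from baseline. Say there that intrahepatic fat means the fat attenuation index, if that is intended.
2. For the month 1 and month 3 arm comparisons in Protocol 4.4, replace the rule 3 fill with a repeated-measures model on the observed fat attenuation values. Patients who miss one intermediate scan still contribute through their other visits, so the patient need not be dropped.
3. Report the number of missed intermediate scans by arm and visit, so that the reader can judge how much this matters and whether missingness looks unbalanced.

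The change is to SAP wording only. It costs a few pairs at months 1 and 3 in section 4.5: at 10% missing, about 4 of 44 (0.10 × 44 = 4.4). Month 6 handling is unaffected.

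### SAP 9.3 fills a missing month 6 result according to the patient's response, and leaves improved patients who drop out with no value

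*SAP*

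**What the plan says.** The primary endpoint in SAP 4.1 is binary: "Effective: fat attenuation index is reduced by a level or more"; anything else is *Invalid*. The visits are fixed: "We will detect the fat attenuation index at 0, 1, 3, 6 months following treatment".

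SAP 9.3 opens with "Results will be carried forward when primary outcome measures are absent, according to the following details" and lists four cases:

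- Rule 1: the month 6 value is missing and "they do not show a response at the cessation of therapy".
- Rule 2: "If patients withdraw from the study before cessation of the study, and continue without a response".
- Rule 3: "If patients lack an intermediate visit of a fat attenuation value, but have results for insulin resistance", gut-barrier and bacterial-overgrowth results; the previous value is used.
- Rule 4: "If patients withdraw from the study because of a full recovery, the results of the last visit can be carried forward".

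Three other places bear on this. SAP 6.1 includes dropouts in the full analysis set and says intention-to-treat will be used when the primary outcome is absent, but assigns no value. SAP 6.2 makes the per-protocol set, which requires completion, the main set for primary efficacy. Protocol section IV, 2.4 lists the reasons for loss: unrelated serious illness, serious side effects, the patient's own request or missed visits, and new interfering medication. Recovery is not among them, and none is linked to SAP 9.3.

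**The concern.** A missing-data rule should not depend on the outcome it is meant to supply. Rules 1 and 2 apply only to patients without a response, and rule 4 only to those called fully recovered. Between them lies a patient who dropped one fat attenuation level, and so met the definition of *Effective*, but was not called recovered and then left or missed month 6. No rule gives that patient a month 6 value. A patient with no scan after baseline is not clearly covered either.

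Rule 4 has two further weaknesses. It assumes that a recovery seen at an earlier visit lasts to month 6. It also rests on an undefined label, given in a trial that SAP 3.1 describes as open-label.

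At stake is the month 6 effective rate in each arm. If the amount of loss or the use of the label differs between arms, the difference between arms is affected too.

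**Working it through.** **Inputs.** SAP 3.4 gives planned rates of 69% (capsules), 44% (metformin and simvastatin) and 10% (TLC), a 25-point target and 10% loss to follow-up. The plan's attrition step reproduces: 44 / 0.90 = 48.9, so 49 per arm, and 4 × 49 = 196. Ten per cent of 49 is about 5 patients per arm.

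**Assumptions.** Month 6 is the deciding visit; SAP 4.1 does not say so, but rule 1 carries values to it. Dropouts respond at the same rate *p* as completers. No dropout is labelled recovered. A patient whom no rule covers leaves the denominator.

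**Literal rules.** With loss *m*, non-responding dropouts stay in as *Invalid* and responding dropouts fall out:

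rate = (1 − m)p / [(1 − m) + m(1 − p)]

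At m = 0.10:

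- Capsules: 0.621 / (0.900 + 0.031) = 66.7%, instead of 69%.
- Active comparators: 0.396 / (0.900 + 0.056) = 41.4%, instead of 44%.
- TLC: 0.090 / (0.900 + 0.090) = 9.1%, instead of 10%.

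The capsule–comparator difference is 25.3 points against a true 25.0.

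**Unequal loss.**

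| Loss, capsules / comparator | Capsules | Comparator | Difference |
|---|---|---|---|
| 5% / 15% | 0.6555/0.9655 = 0.67892 | 0.3740/0.9340 = 0.40043 | 27.8 points |
| 15% / 5% | 0.5865/0.8965 = 0.65421 | 0.4180/0.9780 = 0.42740 | 22.7 points |

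**No true difference (44% in both arms).** Loss of 5% against 15% gives 42.7% and 40.0%, a spurious 2.7 points. Loss of 0% against 20% gives 44.0% and 38.6%, or 5.4 points.

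**Effect of the label.** Keep 44% in both arms and 10% loss in both. If responding dropouts are all called recovered in one arm and none are in the other, the rates are 44.0% and 41.4%, a difference of 2.6 points with no true effect.

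**Bounds at 10% loss.** Counting every dropout as a failure or as a success gives 62.1% to 72.1% for capsules and 39.6% to 49.6% for a comparator. The difference therefore lies between 62.1 − 49.6 = 12.5 and 72.1 − 39.6 = 32.5 points.

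**The case against.** The strongest reply is that SAP 6.2 mainly uses the per-protocol set for primary efficacy. Withdrawals under rules 2 and 4 do not complete the study, so the rules act mainly on the full analysis set. That stands, and it limits the claim: the documents do not show that the main efficacy figure runs through SAP 9.3. It does not remove the problem. A completers' set is itself selected after randomisation, and the SAP does not say which set decides.

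The size is also modest: with equal loss the contrast moves by 0.3 points. That stands too.

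A reader might infer several stronger points that the text does not support:

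- *A shift of 10 points (5/49) in one arm.* This recodes every dropout from failure to success. The rules carry forward a measured result, so a last scan without a one-level fall remains *Invalid*. Choosing between carrying forward and omitting moves a 69% rate by at most 6.9 points (69.0 to 62.1, all non-responders) or 3.1 points (69.0 to 72.1, all recovered). At 44% the figures are 4.4 and 5.6.
- *That carry-forward is optional.* Each rule is worded permissively, but the opening sentence is not: "Results will be carried forward when primary outcome measures are absent, according to the following details". The two wordings need reconciling; optional use is only one reading.
- *That rule 3 shares the fault.* Its condition is the availability of other tests, not response, and it concerns intermediate visits.
- *That the rules are applied with the arm known.* The recovery label is exposed because the trial is open-label. SAP 9.3 does not say who applies the rules, and SAP 8.2 has locked data passed to statistical staff.

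**Conclusion.** The point holds as a defect in a stated rule. Three of the four cases in SAP 9.3 depend on response, one of them on an undefined category, and a group of patients who met the endpoint before leaving has no month 6 value. SAP 6.1 does not close the gap.

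Under the assumptions above, each arm's rate falls by about 1 to 3 points at the planned 10% loss. Differences of 22.7 to 27.8 points replace a true 25.0 when loss is 5% in one arm and 15% in the other. The unequal-loss figures are illustrations; the documents give only the overall 10%. Unequal loss is nevertheless plausible, since side effects are a listed reason for loss and one arm receives lifestyle treatment alone.

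It would be tempting to conclude that the rules favour the capsules. The documents do not support a direction: losing improved leavers lowers a rate, carrying recoveries forward can raise it, and the net effect depends on which arm loses more patients and how the label is used.

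**What to change.** Replace the response-dependent rules with one mandatory rule for all arms:

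- Analyse month 6 *Effective* or *Invalid* in all randomised patients, and state that this set, not the per-protocol set, decides.
- Multiply impute missing month 6 values by arm from the baseline, month 1 and month 3 fat attenuation values. This also covers patients with no scan after baseline.
- Delete the full-recovery rule.
- As sensitivity analyses, report missing counted as not *Effective*, and the best/worst bounds.

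Missing-as-failure is better as a sensitivity analysis than as the primary method. With 44% in both arms and 5% against 15% loss it gives 0.95 × 44 − 0.85 × 44 = 4.4 spurious points, against 2.7 under the present rules. At equal 10% loss it shrinks the planned difference to 62.1 − 39.6 = 22.5 points, with pairwise power of about 61% at 49 per arm (two-sided 0.05).

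The cost is SAP wording and somewhat more analysis. The scans used for imputation are already scheduled. The per-protocol result becomes supportive. Imputation assumes that loss is explained by arm and the earlier scans, which is why the bounds should be reported beside it.
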